8.2.7 Severity Grading and Management of Injection Site Reactions

Injection of a biologic agent carries a potential risk of injection site reaction which is characterized as an intense reaction (usually immunologic) at or near the site of injection. Injection reactions will be graded according to the National Cancer Institute (NCI) Common Terminology Criteria for Adverse Events (CTCAE) version 4.03.

[Table 3](#) outlines the injection site reaction grading system, associated symptoms, and the recommended actions to be taken. For any injection reaction, a serum tryptase level will be measured. Reactions at the INXN-2001 injection site that occur within 24 hours after the injection and are attributed to INXN-2001 will be considered to be injection related AEs.

Table 3. Injection Site Reaction Severity Grading and Management

CTCAE Grade	Symptoms	Course of Action
1	Tenderness with or without associated symptoms (eg, warmth, erythema, itching)	No intervention required.
2	Pain; lipodystrophy; edema; phlebitis	Proceed with further dosing cycles.
3	Ulceration or necrosis; severe tissue damage; operative intervention indicated	Discontinue further study treatment and notify Medical Monitor. Report and manage as DLT: see Section 6.2.4 . If toxicity meets seriousness criteria, immediately report as per SAE reporting procedures; see Section 9.4 .
4	Life-threatening consequences; urgent intervention indicated	Permanently discontinue study treatment and notify Medical Monitor. Report and manage as DLT: see Section 6.2.4 . Defaults to “serious”. Immediately report as per SAE reporting procedures; see Section 9.4 .
5	Death	Immediately notify Medical Monitor and report as per SAE reporting procedures; see Section 9.4 . Discontinue further subject enrollment as per study stopping rules; see Section 6.2.7 .

As with all AEs, injection-related signs or symptoms which, in the Investigator's judgment, are not related to immunologic reactions (eg, dyspepsia, urinary frequency, etc) should be recorded and graded as AEs according to NCI CTCAE v.4.03 criteria in the CRF. Study stopping rules will not apply to a specific event if it is clearly unrelated to INXN-2001 injection (eg, accidental trauma). If an AE associated with injection cannot be definitely shown to be unrelated to INXN-2001, then study stopping rules will apply.

8.2.8 Prophylactic Hydration, Antipyretic and/or Analgesic Administration

The use of antipyretics and/or analgesics and aggressive hydration is allowed anytime during study treatment, as indicated, including prophylactic administration.

Since fever and flu like symptoms are commonly experienced following adenoviral vector administration it is strongly recommended that subjects be treated with prophylactic oral hydration, antipyretic and/or analgesic medications prior to study drug administration.

For those subjects who experience treatment related symptoms (eg, fever, headache, chills, dehydration, etc) during Cycle 1, prophylactic hydration, antipyretic and/or analgesic medications must be given prior to study drug administration in subsequent cycles. Please refer to [Appendix 3](#) for a recommended regimen for the prophylactic hydration and administration of antipyretics and/or analgesics.

8.2.9 Disposition of Unused Study Drug

All unused study drug should be destroyed on site in accordance with applicable site facility and US Occupational Safety and Health Administration (OSHA) procedures after a full accountability has been documented. Any on-site destruction of unused study drug must be documented and the records maintained in the Investigator's study file.

8.3 CONCOMITANT THERAPY

Concomitant medication information, including blood products, vitamins and other supplements, will be collected for the time period beginning 28 days prior to the first dose of study drug through the Post-Treatment Safety Assessment visit. The following medications are or are not permitted:

Permitted:

- Subjects may receive standard treatments, including palliative and supportive care for any underlying illness with the exception of palliative radiotherapy which is NOT permitted.
- Antidiarrheal therapy is permitted for study drug-induced diarrhea.
- Antiemetics are permitted for study drug-induced nausea and vomiting.
- Treatment with vitamin/mineral supplements is acceptable provided that they do not interfere with study endpoints, in the opinion of the investigator.

Not Permitted:

- Subjects may not receive medications, foods or drinks that induce, inhibit, or are substrates of the CYP450 3A4 pathway within 7 days prior to the first dose of study drug through 96 hours after their last dose of INXN-1001. See [Appendix 2](#) for examples.
- Subjects may not receive any other investigational agent or anti-cancer therapy (chemotherapy, radiotherapy, etc) while receiving study treatment.

8.4 EVALUATION AND ASSESSMENT PROCEDURES

8.4.1 Schedule of Assessments

A tabular schedule of evaluations and procedures is provided in [Table 2](#) (Schedule of Assessments).

8.4.2 Safety Evaluations

8.4.2.1 Demographics and Medical History

Each subject's complete medical history will be documented during screening, including demographic information, relevant medical history, current primary cancer diagnosis, and prior cancer treatments (chemo- and immunotherapies, radiation therapy, surgeries). In addition concomitant medications, including blood products, vitamins and other supplements, received during the 28 days prior to initiating study treatment will be recorded.

8.4.2.2 Physical Examinations

A complete physical exam will be performed at Screening and at the Post-Treatment Safety Assessment visits. Symptom-directed physical exams will be performed at Days 1, 8 and 15 of each cycle.

8.4.2.3 ECOG Performance Status

ECOG performance status will be assessed as provided in [Appendix 1](#).

8.4.2.4 Height and Weight

Height (cm) will be measured during screening. Weight (kg) will be measured at screening, Day 1 of each cycle, and at the Post-Treatment Safety Assessment visit.

8.4.2.5 Vital Signs

Vital signs will include blood pressure, pulse, temperature, and respiration. Blood pressure is to be monitored closely to prevent hypotension for up to 72 hours after administration of INXN-1001. Blood pressure assessment is required on Day 3 or Day 4 for Cycle 1 and Cycle 2. Subjects must be instructed to maintain adequate oral hydration on and in between dosing days; sites must closely monitor subjects' hydration status.

8.4.2.6 Adverse Events

Monitoring and recording of adverse events (AEs) and serious adverse events (SAEs) will be conducted throughout the study. AEs/SAEs that occur following informed consent until the Post-Treatment Safety Assessment must be recorded on the AE CRF; AEs/SAEs that occur prior to informed consent should be added to the medical history CRF.

Definitions, documentation, and reporting of AEs and SAEs are described in [Section 9.0](#).

8.4.2.7 Pregnancy Testing

Females of childbearing potential will have a serum pregnancy test at the screening visit and a urine pregnancy test on the first day of each treatment cycle, prior to administration of INXN-1001.

8.4.2.8 Hematology

Hematology tests include: complete blood count and white blood cell count, differential white blood cell count, red blood cell count, hematocrit, hemoglobin, red blood cell indices, reticulocyte count, MCV (mean corpuscular volume) and platelet count. PTT (partial thromboplastin time) and INR (international normalized ratio) will also be evaluated.

8.4.2.9 Serum Chemistry

Serum chemistry tests include: aspartate transaminase (AST), alanine transaminase (ALT), lactate dehydrogenase (LDH), alkaline phosphatase (ALP), creatinine, total bilirubin, total protein, albumin, blood urea nitrogen, glucose, sodium, potassium, chloride, calcium, phosphorus and bicarbonate.

8.4.2.10 Urinalysis

Urinalysis panel (dipstick) includes: appearance, pH, specific gravity, glucose, protein/albumin, blood, ketones, bilirubin, nitrates, and leukocyte esterase. In addition, a microscopic exam for casts, crystals, and cells may be done if clinically indicated.

8.4.2.11 Electrocardiogram (ECGs)

A standard, single 12-lead ECG for local safety assessment will be done at screening, 2½ to 3 hours after INXN-1001 dosing (prior to INXN-2001 injection) on Day 1 of each cycle, and at the Post-Treatment Safety Assessment visit. The ECGs will be used to evaluate the QT/QTc interval.

8.4.2.12 Serum Tryptase

A serum tryptase level will be obtained upon the occurrence of a suspected injection reaction and/or hypersensitivity reaction.

8.4.2.13 Immune Response Analyses

Blood samples will be collected from the subjects at specified visits to evaluate the potential antibody and cellular immune response to INXN-2001 (adenovirus and, RTS [] components) and melanoma-associated antigens. []

Plasma

and/or serum cytokine levels (eg, IL-12, IFN- γ , etc) will be assayed using multiplex and/or ELISA methodology. One or more serum cytokines may be assessed in as close to real time as possible for one or more time points in a dosing cycle at the request of the Medical Monitor or other sponsor representative(s).

In addition to these planned analyses, []

8.4.3 INXN-1001 Pharmacokinetic Assessment

Subjects will undergo an INXN-1001 pharmacokinetic (PK) assessment during Cycle 1 of their study treatment. Whole blood samples will be collected on Day 1, Day 2, Day 7, and Day 15 as defined in the Schedule of Assessments (see [Table 2](#)).

8.4.4 Efficacy Assessments

Appropriate cancer staging procedures should be performed during screening. For the purpose of this clinical trial, the following imaging is expected at screening:

- a. CT of the chest, and CT (or MRI) of the abdomen and pelvis
- b. MRI (or CT) of the brain if brain metastasis are known or suspected
- c. CT or MRI of other anatomical regions as clinically indicated

For subjects with measurable lesions, target lesions should be selected and measured as per RECIST 1.1 guidelines.¹ Lesions that will be/are injected with INXN-2001 and/or biopsied should not be selected as target lesions, but should be measured (if measurable).

For each subject, disease sites are to be assessed throughout the study using the same method(s) of assessment used at screening. Specific image acquisition guidelines will be provided by a central imaging laboratory. Chest, abdomen, pelvis imaging is required for all follow-up imaging time points; images of the brain and other anatomical regions should be acquired on follow-up if positive at screening and as clinically indicated.

All subjects will have tumor response assessments performed including Cycle 3 Day 13, the Post-Treatment Safety Assessment visit (28 ± 3 days following the last dose of INXN-1001) or at the time of early withdrawal from study treatment and again at the Follow-Up Tumor Assessment visit (35 ± 7 days following the Post-Treatment Safety Assessment visit). The Investigator will evaluate each subject for response to therapy according to RECIST 1.1 guidelines.¹ Subjects without objective evidence of disease progression at the Follow-Up Tumor Assessment visit should continue to have tumor assessments performed at 8-10 week intervals until disease progression has been documented or an alternate anti-cancer therapy has been initiated, whichever occurs first.

In addition to radiological imaging techniques, photographs of visible cutaneous lesions should also be obtained. Digital photograph(s) with included measuring tape should be taken of all visible injected tumor(s) and non-injected tumors, and of any remaining visible local reactions in or around the injected lesion(s). Any subject who has or develops vitiligo, should be documented the same way. Details regarding photographic methodology will be provided in the Photography Operations Manual.

As a supplement to the standard RECIST v1.1 guidelines established to evaluate anti-tumor responses to chemotherapeutic agents, the sponsor will be analyzing anti-tumor response by assessing total tumor burden over time. Please refer to Appendix 4 for a description of “immune-related Response Criteria” (irRC).

8.4.5 Assessments of Transgene Function, Immunological Activities and Biological Effects

8.4.5.1 Transgene Function

Punch biopsies of the tumor(s) and/or associated tumor involved draining lymph nodes will be collected for *in vivo* assessment of the presence of the adenoviral vector, possible ongoing transgene expression of hIL-12, and expression of IL-12-induced down-stream genes. The presence of the adenoviral vector will be assessed either by quantitative PCR using primer-specific probes for the RTS- switch components, to distinguish between exogenous versus endogenous adenovirus, or by IHC. Expression of IL-12 and IL-12-induced gene expression will be evaluated via qRT-PCR, using a panel of known IL-12-regulated genes in melanoma as well as signaling pathways downstream from IL-12.

The tumor biopsies will be analyzed with appropriately designed primers, including genes known to be regulated by IL-12. If sufficient material is available, microarray analyses may be performed to evaluate global changes in gene expression profiles after treatment.

8.4.5.2 Immunological Activities

Part of the biopsied tumor(s) will be evaluated by standard light microscopy and immunohistochemistry to assess cellular infiltration in the tumor. Cellular infiltration by effector cells, such as T cells and their subsets (CD4+, CD8+ and CTLs as assessed by granzyme B expression) and NK cells, will be evaluated as well as immune suppressor elements, such as T-regulatory cells (Tregs). Biopsy specimens will also be evaluated for IL-12 expression and markers of immune activation. Biopsy sections will be read by a pathologist who is unaware of study subject background and subjected to automated enumeration of positively staining cells. Blood will be drawn for assessing cell-mediated immunity, especially frequency of CTLs and Tregs. Unseparated peripheral blood mononuclear cells will be tested by flow cytometry for the relative percentages of immune cells, and if possible for intracellular IFN- γ , other cytokines and granzyme B, as characteristics of CTL, both directly after isolation and after in vitro stimulation with autologous DCs transduced by adenoviral vectors expressing major melanoma specific antigens. Unseparated peripheral blood mononuclear cells will also be stimulated with autologous DCs transduced by adenoviral vectors expressing major melanoma specific antigens in IFN- γ ELISPOT and/or flow cytometric intracellular staining for IFN- γ and other relevant cytokines, to enumerate the anti-melanoma-CTLs.

9. ADVERSE EVENTS

9.1 ADVERSE EVENT (AE) DEFINITION

An adverse event is any untoward medical occurrence associated with the use of a drug in humans whether or not considered drug related. Any worsening of a preexisting condition, which is temporally associated with the use of the study drug, is also an AE.

Adverse events include:

- Suspected adverse drug reactions;
- Reactions from study drug overdose, abuse, withdrawal, sensitivity, or toxicity;
- Significant changes or abnormalities when compared to baseline, in signs, symptoms, clinical laboratory results, or physiological testing. This includes any worsening of a preexisting condition temporally associated with the use of study drug;
- Other untoward medical events, regardless of their relationship to the study drug, such as injury, events that require surgery, accidents, extensions of symptoms, or apparently unrelated illnesses.

The following considerations apply when identifying an AE:

- Anticipated day-to-day fluctuations of pre-existing conditions including the disease under study that do not represent a clinically significant exacerbation or worsening need not be considered adverse events.
- In the event that a constellation of symptoms results in a confirmed diagnosis, the diagnosis (not the symptoms) should be recorded as the adverse event term.
- If a diagnosis cannot be established, the symptoms should be recorded as the adverse event(s).
- If an ongoing symptom has been included in the medical history, an associated severity grade and frequency should also be documented so that a worsening in severity or frequency of a symptom can be readily identified as an AE.
- Progression of disease is not itself an AE however, the presenting sign or symptom of the disease progression should be documented as an AE (eg, increase in pain).
Exception: If a subject experiences progression of disease that results in death, 'progression of disease' may be reported as an SAE if, by medical opinion, the term best describes the cause of death.

9.2 EVALUATION OF ADVERSE EVENTS (AEs)

9.2.1 Determination of Seriousness

The Investigator will determine the seriousness of an AE based on the following:

9.2.1.1 Serious Adverse Event (SAE)

An AE is considered an SAE if at least one of the following conditions applies:

- Death: An AE that results in death during the active study period or within 30 days following Study Drug administration. In addition, a reported death at any time post-study that is thought to be related to Study Drug administration;
- Life-threatening adverse event: An AE that places the patient, in the view of the Investigator, at immediate risk of death from the event as it occurred (ie, this does not include a reaction that had it occurred in a more severe form, might have caused death);
- Permanent, persistent, or significant disability: A disability is defined as any substantial disruption of a person's ability to conduct normal life functions;
- Inpatient hospitalization or prolongation of existing hospitalization: In general, hospitalization refers to admission of a patient into a hospital for at least a 24-hour stay. Hospitalizations for routine blood transfusions, hospitalization for an elective or diagnostic procedure, or surgery for a pre-existing condition that has not worsened, are not considered SAEs. (Emergency Room visits that do not result with admission are not considered as SAEs);
- A congenital anomaly/birth defect: A fixed, permanent impairment established at or before birth;
- Important medical event: Events that may not result in death, be life-threatening, or require hospitalization may be considered SAEs when, based upon appropriate medical judgment, they jeopardize the patient and require medical or surgical intervention to prevent a life-threatening situation, hospitalization or death;
- New Cancer: Occurrence or diagnosis of a new cancer during the trial is considered a serious adverse event. (This does not pertain to metastasis of current disease);
- Any AE associated with an overdose of the study drug: An overdose of study drug is defined as an occurrence of administered dose exceeding that which is prescribed by the Investigator per protocol.

9.2.1.2 Non-Serious Adverse Event

Adverse events that do not fulfill the previous criteria are classified as non-serious AEs.

9.2.2 Determination of Severity

The severity of AEs will be assessed according to the NCI CTCAE, v. 4.03. If the AE is not defined in the NCI CTCAE, v. 4.03, the Investigator will determine the severity of an AE based on the following definitions:

- **Mild (Grade 1)**: The AE is noticeable to the patient, but does not interfere with routine activity. The AE does not require discontinuing administration or reducing the dose of the study drug.
- **Moderate (Grade 2)**: The AE interferes with routine activity, but responds to symptomatic therapy or rest. The AE may require reducing the dose, but not

discontinuing administration of the study drug.

- Severe (Grade 3): The AE significantly limits the patient's ability to perform routine activities despite symptomatic therapy. In addition, the AE leads to discontinuing administration or reducing the dose of the study drug.
- Life Threatening (Grade 4): The AE requires discontinuing administration of the study drug. The patient is at immediate risk of death.
- Death (Grade 5): The patient dies as a direct result of the complication or condition

Adverse events should be reported using the maximum intensity of the event (eg, if a subject reported nausea lasting 3 days, one start date and stop date should be recorded along with the maximum intensity experienced for that event over that 3 day timeframe).

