6.2.4 Definition and Management of Dose-Limiting Toxicity (DLT)

Dose-limiting toxicity (DLT) is defined as:

- Any injection site reaction that includes ulceration, necrosis, severe tissue damage or where operative intervention is required.
- Any local or systemic injection reaction that has life-threatening consequences, requires urgent intervention or results in death.

- Any study drug-related \geq Grade 3 adverse event, except nausea and/or vomiting in subjects who did not receive optimal treatment with anti-emetics.

Phase I and Phase II, Group 1: If DLTs have been observed in >1 of the 3-6 subjects in a cohort during the first treatment cycle, the MTD will have been exceeded and further use of that dose will be discontinued in all subjects, and the next lower dose cohort will be assessed as to whether it meets the definition of the MTD.

Phase II, Group 2: If an adverse event that meets the Phase I DLT definition is observed in >1 of the 3-6 subjects in Group 2 during the first treatment cycle, the SRC will convene to discuss reduction in dose and/or change to posology and the cohort will be expanded by 3 subjects. The recommended Phase II dose will be the dosage and posology where ≤ 1 of 3 to 6 subjects experiences an adverse event as described in the definition of DLT.

The Medical Monitor should be immediately notified of any potential DLT. Subjects will be withdrawn from study treatment if they experience an injection site reaction that meets DLT criteria or other Grade 3 toxicity related to study drug that, upon review of the SRC, is deemed to be a DLT. If, however, the subject has experienced a substantial benefit from treatment and the SRC recommends continuation on the study, re-exposure to the experimental treatment may proceed at a lower dose of INXN-1001 on a case by case basis. Any subject who experiences a Grade 4 toxicity related to study treatment will be withdrawn from study.

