8.2.6 Retreatment Criteria, Dose Delays and Modifications

Subjects may receive up to 6 cycles of study drug treatment. In order to receive each repeat treatment cycle, all treatment-related adverse events must have resolved to Grade 1 or baseline and the following laboratory criteria must be met:

- Hemoglobin ≥ 9 g/L
- Lymphocytes $> 700/\text{mm}^3$
- Neutrophils $\geq 1,500/\text{mm}^3$
- Platelets $\geq 100,000/\text{mm}^3$
- Serum creatinine $\leq 1.5 \times \text{ULN}$
- AST and ALT $\leq 2.5 \times \text{ULN}$. For subjects with documented liver metastases, ALT and AST $\leq 5 \times \text{ULN}$
- Total bilirubin $< 1.5 \times \text{ULN}$
- INR and PTT $< 1.5 \times \text{ULN}$, if not therapeutically anticoagulated.

Clinical laboratory tests drawn for analysis on Day 15 of each cycle may be used for determining if the retreatment criteria have been met, and must be reviewed by the investigator or designee prior to the next cycle of study drug administration. Treatment delays to allow for recovery to acceptable levels are allowed at weekly intervals up to a maximum of 4 weeks. In the event that a treatment-related dose delay is necessary, then the next cycle of study treatment will be administered at the next lower INXN-1001 dose level. Subjects in the first dose cohort who do not meet the retreatment criteria will be discontinued from study treatment (ie, no dose reductions are permitted).

Subjects who experience a DLT will be managed as described in [Section 6.2.4](#). Subjects who experience an injection site reaction should be managed as described in [Section 8.2.7](#).

Subjects who experience a treatment-related Grade 3 adverse event, other than nausea and/or vomiting in the absence of optimal treatment with anti-emetics, will be discontinued from study treatment. If, however, the subject has experienced a substantial benefit from treatment and the SRC recommends continuation on the study, re-exposure to the experimental treatment may proceed on a case by case basis.

Subjects who experienced a Grade 4 treatment-related adverse event at any time during study treatment must be discontinued from study treatment.

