9.3 DOCUMENTING ADVERSE EVENTS (AES)

All AEs (including SAEs) are to be accurately recorded on the Adverse Event page of the patient's eCRF from the time the patient signs the informed consent until the post-treatment safety visit. Each event will be assessed for serious criteria, severity, and causality (See "Causality Assessments"). The date of onset, as well as the duration of the event will be recorded. In addition, treatments provided to the patient, actions taken with the study drugs, and the outcome of the AE will also be noted.

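### For adverse events outside CTCAE, Grade 3 also requires that study drug was stopped or reduced, so a severe event with no drug action fits no grade and can be left out of the Grade 3+ tables

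*Protocol*

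**What the plan says.** Protocol section 9.2.2 grades severity by CTCAE v4.03 and adds a fallback: "If the AE is not defined in the NCI CTCAE, v. 4.03, the Investigator will determine the severity of an AE" from five definitions written in the protocol.

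- Grade 2: "The AE interferes with routine activity, but responds to symptomatic therapy or rest". Such an event may call for a dose reduction, but not for stopping drug.
- Grade 3: "The AE significantly limits the patient's ability to perform routine activities despite symptomatic therapy". A second sentence follows: "In addition, the AE leads to discontinuing administration or reducing the dose of the study drug".
- Grade 4: "The AE requires discontinuing administration of the study drug. The patient is at immediate risk of death".

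Other sections then use the grade:

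- Section 6.2.4 makes a DLT of any study drug-related Grade 3 or higher "adverse event, except nausea and/or vomiting in subjects who did not receive optimal treatment with anti-emetics".
- Section 8.2.6 takes off study treatment "Subjects who experience a treatment-related Grade 3 adverse event, other than nausea and/or vomiting" without optimal anti-emetics, unless the SRC recommends continuing.
- SAP section 12.2 tabulates Grade 3 or higher events, all (Table 14.3.2.7) and drug-related (Table 14.3.2.8).

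Protocol section 9.3 already records the drug action as an item separate from severity: "actions taken with the study drugs, and the outcome of the AE will also be noted".

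**The concern.** A severity grade should describe the event. Here the fallback Grade 3 depends partly on what was done with study drug, while sections 6.2.4 and 8.2.6 expect the grade to settle what is done. Two subjects with the same clinical event can then be graded differently because their dosing was handled differently. A subject with no dosing left to change cannot meet the Grade 3 wording at all.

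Safety and tolerability is the primary objective. Grade 3 or higher, with relatedness, feeds the DLT definition, the SRC's review and two safety tables. Grades assigned after dosing also have consequences: sections 6.2.5 and 6.2.7 let the SRC reconsider the MTD on events meeting DLT criteria after Cycle 1, and the stopping rules in 6.2.7 run to the post-treatment visit.

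**Working it through.** The plan states no figure on this point, so the check is first a logic test of the definitions and then a day count.

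**Logic test.** Take two events that CTCAE does not define.

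- Record A: severe, not life-threatening, limits activity despite symptomatic treatment, no action on study drug.
- Record B: moderate, responds to symptomatic treatment, and itself leads to stopping drug.

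| Grade in 9.2.2 | Record A | Record B |
|---|---|---|
| 1: no interference with activity | fails | fails |
| 2: interferes but responds; stopping excluded | fails: does not respond | fails: drug was stopped |
| 3: limits activity despite treatment, and leads to stopping or reduction | fails second condition | fails first condition |
| 4: immediate risk of death, stopping required | fails | fails |
| 5: death | fails | fails |

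Neither record fits any grade, and no other section waives the second condition of Grade 3.

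**Where Record A arises.**

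1. After planned dosing has ended. AEs are recorded until the safety visit, 28 ± 3 days after the last INXN-1001 dose (section 9.3; Table 2, footnote 28).
2. Before the first dose. AEs are recorded from consent (section 9.3). Table 14.3.2.7 is not restricted to treatment-emergent events, so these count for subjects who go on to enter the Safety Population.
3. Unrelated events with dosing unchanged. Section 8.2.6 requires stopping only for treatment-related Grade 3 events.

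Settings 2 and 3 can affect only Table 14.3.2.7. A related event in setting 1 can also be missed in Table 14.3.2.8 and in the SRC's review against DLT criteria.

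**Circularity.** Take a related event that limits activity despite treatment, during dosing. If drug is stopped, the event meets Grade 3, and 8.2.6 then calls for stopping. If drug is not changed, Grade 3 is not met, and 8.2.6 is not triggered. Both outcomes agree with the text. Under the grade-based DLT criterion the event is a DLT in the first case and not in the second.

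**Time after the last dose, six cycles completed, no delays.**

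- Day of last dose = 5 × cycle length + last dosing day of the cycle.
- Share = 28 / (day of last dose + 28).
- Daily: 5 × 21 + 7 = 112; 28/140 = 20.0%. With the ± 3-day window: 25/137 = 18.2% to 31/143 = 21.7%.
- Every other day: 5 × 28 + 13 = 153; 28/181 = 15.5%. With the window: 25/178 = 14.0% to 31/184 = 16.8%.
- Counting 28 screening days as well: 28/168 = 16.7% and 28/209 = 13.4%.

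These are shares of observation time. They are not shares of events.

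**Effect of one omitted subject.** SAP section 1.0 gives cohorts of 3, 3, 3 and 4 in Phase I and 4, 4, 3 and 2 in Phase II. One subject is 1/4 = 25 to 1/2 = 50 percentage points of a cohort's Grade 3+ proportion, if such an event exists and the subject has no other Grade 3+ event.

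**The case against.** The strongest reply is that this will rarely matter. CTCAE governs by default. Injection site reactions have their own grading (Table 3). Two of the three DLT criteria in 6.2.4 do not use the grade. Any potential DLT goes to the Medical Monitor, and in Phase I the SRC also reviews the overall occurrence of AEs (Appendix 5). Seriousness does not depend on grade, and SAP section 12.2 lists all AEs. All of that stands and limits the reach.

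It can also be argued that the second sentence of Grade 3 only describes a usual consequence. The text does not favour this: Grade 2 says what an event may call for, whereas Grade 3 joins a statement of fact to the clinical condition.

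The objection also disposes of four stronger readings that a reader might draw:

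- **That a moderate event which stops drug is pushed up to Grade 3 and counted as a DLT.** It fails Grade 3's first condition, so it is ungraded. If drug was stopped for another reason, the event did not lead to it and can stay Grade 2.
- **That no event after the most recent dose can reach Grade 3.** An event in the gap between cycles can itself lead to reduction or discontinuation. The gap exists only when no further dosing is planned. MTD-defining DLTs belong to Cycle 1, when later cycles are normally still planned.
- **That the text forces a lower grade.** It supplies no grade, and the investigator has to resolve that.
- **That the post-dose share is much larger with fewer cycles.** Such figures ignore that an event before the next due cycle can itself end treatment, and that the safety visit may take place at early withdrawal (Table 2, footnote 28). Only the six-cycle shares are usable.

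**Conclusion.** The defect is real and narrow. For events outside CTCAE, section 9.2.2 mixes clinical intensity with drug action, is circular with 6.2.4 and 8.2.6, and leaves both records tested above without a grade. The likely harm is omission of severe events from Table 14.3.2.7 and, for related events after dosing, from Table 14.3.2.8 and the SRC's later review. Systematic over-grading and a distorted Cycle 1 DLT count are not shown.

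The number of affected events cannot be derived from the documents and may be zero. The time in which the post-dosing gap can arise is 20.0% (daily) or 15.5% (every other day) of the period from first dose to safety visit, assuming six completed cycles without delay. The reading also assumes that fallback grades enter the same tables as CTCAE grades. SAP section 12.0 names only CTCAE v4.03 and does not say.

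**What to change.** In section 9.2.2, define the fallback grades by clinical intensity only: effect on activity, response to symptomatic treatment, and immediate risk of death. Keep action taken with study drug as the separate CRF item of section 9.3. Reconcile 9.2.2 with 6.2.4 and 8.2.6 so that they do not define each other; this point proposes no dose or stopping rule.

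Before database lock, identify the AEs graded on the fallback scale and re-check their grades. No document describes a CRF flag for them, so this means comparing AE terms with CTCAE v4.03.

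The cost is a wording change and a small retrospective check of grades. The SAP reports 13 + 13 = 26 patients as already treated, so the check is the part with practical effect. The drug-action field already exists, and no new data item is needed.
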